Institution/Department : Kaohsiung Veterans General Hospital

Principal Investigator (PI) : [name]

Research Project Title : A prospective randomized trial of levofloxacin-amoxicillin triple therapy vs. levofloxacin-tetracycline quadruple therapy in second-line *Helicobacter pylori* treatment

NCT Number : NCT02978157

Date of the document : 2017/09/30

ABSTRACT

Background: Although proton pump inhibitor (PPI) -amoxicillin-levofloxacin triple therapy has been recommended by the Maastricht IV/Florence Consensus Report for rescue treatment of both standard triple therapy and non-bismuth quadruple therapy, the eradication rates of the rescue treatment for standard triple therapy and non-bismuth quadruple therapy by intention-to-treat analysis are only 66.9% and 77.5%, respectively. It is therefore mandatory and urgent to develop a highly effective rescue therapy for second-line treatment of *H pylori* infection. From the profiles of antibiotic susceptibility data following eradication therapy, tetracycline, amoxicillin and levofloxacin are all good candidates of antibiotics used in the rescue treatment for both standard triple therapy and non-bismuth quadruple therapy. Our recent study also revealed that PPI- bismuth-tetracycline-levofloxacin rescue treatment might achieve a very high eradication rate 96% for *H pylori* infection after failure of non-bismuth quadruple therapy.

Aims: To investigate (1) the efficacy of PPI- bismuth -levofloxain-tetracycline quadruple therapy and PPI-amoxicillin-levofloxacin triple therapy in rescue treatment for *H pylori* infection, and (2) the bacterial and host factors determining the efficacy of PPI-bismuth-levofloxain-tetracycline quadruple therapy and PPI-amoxicillin-levofloxacin triple therapy.

Methods: Consecutive 164 *H pylori*-infected adult patients with failure of first-line therapies are randomly assigned to either EBLT (esomeprazole 40 mg b.d., bismuth 120 mg q.d.s., levofloxacin 500 mg o.d., and tetracycline 500 mg q.d.s.) therapy or EAL (esomeprazole 40 mg b.d., amoxicillin

In clinical practice, the regimen for second-line therapy of *H pylori* infection depends on the regimen used in first-line therapy. After failure of a standard triple therapy, either a bismuth-containing quadruple therapy or PPI-amoxicillin-levofloxacin triple therapy is recommended [15]. Bismuth-containing quadruple therapy regimen fails in 5-63% of patients with an average eradication rate of 76% on the basis of a pooled analysis [16-18]. PPI-amoxicillin-levofloxacin has been recommended as an encouraging strategy for second-line therapy [19]. A meta-analysis by Saad et al. [19] showed that a 10-day regimen of levofloxacin-based triple therapy was superior to 7-day bismuth-based quadruple therapy. However, levofloxacin-based triple therapies seem less effective in Asia. Our recent study showed that PPI-amoxicillin-levofloxacin triple therapy only achieved a 69.9% eradication rate for rescue treatment of standard triple therapy in Taiwan [20].

Currently, the best second-line therapy after failure of non-bismuth quadruple therapies (such as sequential therapy, concomitant therapy or hybrid therapy) remains unclear. Although PPI-amoxicillin-levofloxacin triple therapy also has been recommended by the Maastricht IV/Florence Consensus Report as a rescue treatment for sequential therapy [15], the mean eradication rate of the rescue regimen is suboptimal (mean, 77.5% [79/102]; range: 50% [3/6] to 100% [7/7]) [21-25].

Antibiotic resistance is the key factor determining the outcome of rescue treatment for anti-*H pylori* therapy. According to our previous reports [20,26], the drug resistant rates to tetracycline, levofloxacin, amoxicillin, clarithromycin and metronidazole were 0%, 21%, 6%, 59% and 57% respectively following standard triple therapy [20] and 0%, 25%, 0%, 75% and 75% respectively following sequential therapy [26]. The data indicate that tetracycline, amoxicillin and levofloxacin are good candidates of antibiotics used in the rescue treatment for both standard triple therapy and non-bismuth quadruple therapy (such as sequential therapy, concomitant therapy and hybrid therapy).

Although PPI-amoxicillin-levofloxacin triple therapy has been recommended by the Maastricht IV/Florence Consensus Report for rescue treatment of both standard triple therapy

and non-bismuth quadruple therapy [15], the eradication rates of the rescue treatment for standard triple therapy and sequential therapy by intention-to-treat analysis are only 66.9% [20] and 77.5% [23], respectively. Our recent study also revealed that PPI- bismuth-tetracycline-levofloxacin rescue treatment might achieve a very high eradication rate (96%) for *H pylori* infection after failure of non-bismuth quadruple therapy [26]. We therefore design the prospective, multicenter, randomized controlled trial to investigate (1) the efficacy of PPI-bismuth-levofloxacin-tetracycline quadruple therapy and PPI-amoxicillin-levofloxacin triple therapy in rescue treatment for standard triple therapy, (2) the efficacy of PPI-bismuth-levofloxacin-tetracycline quadruple therapy and PPI-amoxicillin-levofloxacin triple therapy in rescue treatment for nonbismuth-containing quadruple therapy (such as sequential therapy, concomitant therapy and hybrid therapy), and (3) the bacterial and host factors determining the efficacy of PPI- bismuth- levofloxacin-tetracycline quadruple therapy and PPI-amoxicillin-levofloxacin triple therapy.

REFERENCES

7. Fock KM, Katelaris P, Sugano K, et al. Second Asia-Pacific Consensus Guidelines for

Helicobacter pylori infection. *J Gastroenterol Hepatol* 2009;24:1587-600.

Consecutive 164 *H pylori*-infected adult patients (≥ 20 years old) with failure of first-line therapy for *H pylori* infection will be enrolled for this study after giving informed consent. The presence of *H pylori* after a previous eradication therapy is defined as (1) positive results of both rapid urease test and histology, (2) a positive result of ^{13}C urea breath test, or (3) a positive result of culture. Criteria for exclusion included (a) ingestion of antibiotics, bismuth, or PPI within the prior 4 weeks, (b) patients with allergic history to the medications used, (c) patients with previous gastric surgery, (d) the coexistence of serious concomitant illness (for example, decompensated liver cirrhosis, uremia), and (e) pregnant women.

Methods

Using a computer-generated number sequence, the eligible patients are randomized to either EBTL (esomeprazole 40 mg b.d., bismuth 120 mg q.d.s., levofloxacin 500 mg o.d., and

tetracycline 500 mg q.d.s.) therapy or EAL (esomeprazole 40 mg b.d., amoxicillin 500 mg q.d.s., and levofloxacin 500 mg o.d.) for 10 days. All drugs are taken one hour before meals or night sleep.

Patients are asked to return at the 2nd week to assess drug compliance and adverse events.

To assess eradication efficacy, ¹³C urea breath tests are conducted to assess *H. pylori* status.

Demographic data

A complete medical history and demographic data are obtained from each patient, including age, sex, medical history, history of smoking, alcohol, coffee and tea consumption. Smoking was defined as consumption of cigarettes 1 pack or more per week. Coffee or tea consumption is defined as drinking 1 cup or more per day.

Adverse events are prospectively evaluated. The adverse events are assessed according to a 4-point scale system: none; mild (discomfort annoying but not interfering with daily life); moderate (discomfort sufficient to interfere with daily life); and severe (discomfort resulting in discontinuation of eradication therapy) [26,27]. Compliance is checked by counting unused medication at the completion of treatment. Poor compliance is defined as taking less than 80% of the total medication.

Histological examination

Two biopsy specimens are taken from the lesser curvature sites of the antrum and the corpus, respectively. They are fixed in 10% buffered formalin, embedded in paraffin, and sectioned. The sections, 4- μ m thick, are stained with a haematoxylin and eosion stain and a modified Giemsa stain to observe the presence of curved rod shape bacteria on the mucosal surface [28]. Biopsy specimens are assessed by a histopathologist ([name]), blinded to patient status and the results of other laboratory tests.

Urea breath test

The urea breath test is performed according to our previous studies [29,30]. The staffs who are

blind to the *H pylori* status perform the tests.

Culture and antimicrobial resistance

One antral gastric biopsy specimen is obtained for isolation of *H pylori*, using previously described culture methods [14]. All stock cultures are maintained at -80°C in Brucella broth (Difco, Detroit, MI) supplemented with 20% glycerol (Sigma Chem. Co. St. Louis, MO). The organisms are identified as *H pylori* by Gram staining, colony morphology, and positive oxidase, catalase, and urease reactions. As previously described in more detail [8], the antibiotic susceptibility is tested by E test (AB Biodisk, Solna, Sweden). *H pylori* strains with a MIC value > 0.5 µg/mL, > 1 µg/mL, > 4 µg/mL, > 8 µg/mL and > 1 µg/mL are considered to be resistant to amoxicillin, levofloxacin, tetracycline, metronidazole and clarithromycin, respectively [14,16].

Genotyping of *CYP2C19*

Blood sampling for genotyping of *CYP2C19* is carried out before endoscopy for the subjects who provide informed consent for genetic study. The *CYP2C19* genotype is determined using the polymerase chain reaction-restriction fragment length polymorphism (PCR-RFLP) [31]. A two single-tube tetra-primer PCR assays is applied to detect the *CYP2C19*2* and the **3* allele, respectively. To genotype the *CYP2C19*2* polymorphism, four primers (Table 1) are combined in one tetra-primer PCR assay. Amplification of *CYP2C19* exon 5 with primers Ex5U and Ex5L produced a 321-bp product that served as internal control for the quality of the PCR amplification and as template for the allele-specific amplification (ASA). ASA produced the 229-bp PCR product specific for the **2* allele and the 127-bp PCR product specific for the wild-type allele. The tetra-primer PCR produced amplification of the 309-bp *CYP2C19* exon 4 region (Ex4U and Ex4L), and ASA (**3mutU* and **3wtL*) produced the 110-bp PCR product for the **3* allele and the 228-bp PCR product for the wild-type allele. The following reaction mixture was prepared for the tetra-primer PCR assay to genotype *CYP2C19*2*: 16.4 mL of water, 2.5 mL of buffer 1 (1.5 mM MgCl₂), 0.2 mL of Gold Taq (5 U/mL), 0.5 mL of dNTP mixture (10 mM), 0.4 mL of Ex5U (10 mM), 0.5 mL of Ex5L (10 mM), 0.75 mL of **2mutU* (10 mM), 0.75 mL of **2wtL* (10 mM), and 3.0 mL of genomic

DNA (50 ng/mL). The following cycling conditions were used: 10 min at 94 °C; 44 cycles of 94 °C for 30 s, 50 °C for 30 s, and 72 °C for 60 s; and a final extension of 7 min at 72 °C. Separation by 2% agarose gel electrophoresis and ethidium bromide staining allowed identification of the three PCR products and the interpretation of the *CYP2C19*2* genotype.

Table 1. Oligonucleotides used in this study.

Primer	5' position ^a	Sequence ^b	3' position ^a
Exon 5			
2C19Ex5U ^c	8	CAGAGCTTGGCATATTGTATC	28
2C19Ex5L ^c	328	GTAAACACACA ^c ACTAGTCAATG	307
2C19*2mutU	100	ATCATTGATTATTTCCCA ^d	117
2C19*2wtL	134	AATTGTTATGGGTTCCC	117
Exon 4			
2C19Ex4U ^e	21	TATGAAGTGT ^c TTATATCTAATGTTACTCA	51
2C19Ex4L ^f	329	ACTTCAGGGCTTGGTCAATATAGA	306
2C19*3mutU	220	GTAAGCACCCCTGA	234
2C19*3wtL	248	GGCCTTACCTGGATC	234

Genotypes are classified into three groups: homEM (*CYP2C19*1/CYP2C19*1*); hetEM (*CYP2C19*1/CYP2C19*2* and *CYP2C19*1/CYP2C19*3*); PM (*CYP2C19*2/CYP2C19*2*, *CYP2C19*2/CYP2C19*3*, and *CYP2C19*3/CYP2C19*3*).

Statistical analysis

The primary outcome variable is eradication rate. The secondary outcome variables are the rate of adverse events and compliance. Chi-square test with or without Yates correction for continuity and Fisher's exact test are used when appropriate to compare the major outcomes between groups using the SPSS program (version 10.1, Chicago, Illinois, USA). A *P* value less than 0.05 is considered statistically significant. The sample size is estimated 164 (82 subjects per group) in order to detect a difference of 10% in the eradication rate between the EAL therapy (assumed eradication rate of 70%) and the EBTL therapy (assumed eradication rate of 80%) for rescue treatment.

Eradication rates are evaluated by ITT and per-protocol (PP) analyses. ITT analysis includes all randomized patients who have taken at least one dose of study medication. Patients whose infection status is unknown following treatment are considered treatment failures for the purposes of ITT analysis. The PP analysis excludes the patients with unknown *H. pylori* status following therapy and those with major protocol violations.

To determine the independent factors affecting the treatment response, Host and bacterial

parameters are analyzed by univariate analysis. These variables include the following: age (<60 or \geq 60 years), gender, history of smoking, history of alcohol consumption (<80 g/day or \geq 80 g/day), ingestion of coffee (<1 cup/day or \geq 1 cup/day), ingestion of tea ((<1 cup/day or \geq 1 cup/day), coexistence of a systemic disease (yes or no), previous history of peptic ulcer disease, endoscopic appearance (ulcer or gastritis), CYP2C19 polymorphism, drug compliance (good or poor), and antibiotic susceptibility. Those variables found to be significant by univariate analysis are subsequently assessed by a stepwise logistic regression method to identify independent factors for eradication outcome.

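### Age is analysed only as under 60 versus 60 or over, with no reason given; if its effect is roughly linear, the cut makes the univariate screen more likely to miss it

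*Combined protocol and SAP*

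**What the plan says.** Under Demographic data, age is recorded for everyone: "A complete medical history and demographic data are obtained from each patient, including age, sex". Nothing suggests that it is stored only in bands. The Patients section sets a lower limit, "adult patients (≥ 20 years old) with failure of first-line therapy", and gives no upper limit, expected mean, SD or share aged 60 or over.

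The factor analysis is described at the end of Statistical analysis. Its list begins "These variables include the following: age (<60 or", the second class being 60 years and above. No analysis of age in years is planned. Entry to the multivariable model is then conditional: "Those variables found to be significant by univariate analysis are subsequently assessed by a stepwise logistic regression method". The only significance level in the plan is a P "value less than 0.05 is considered statistically significant". Its sidedness is not stated.

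Finding the host and bacterial factors behind treatment success is a stated objective: the second aim in the Abstract and the third in the Introduction.

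**The concern.** A two-class version of age treats patients aged 21 and 59 as alike and patients aged 59 and 61 as different. If the chance of eradication changes gradually with age, most of that gradient lies within the two classes and is thrown away.

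The loss matters more here than in an analysis that keeps every covariate, because the univariate test acts as a gate. A factor that misses P<0.05 is not considered further, so reduced power in that test can remove age from the model altogether. At stake is the reliability of the factor analysis, for age in particular.

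**Working it through.** The plan states no figure for this analysis, so there is nothing of its own to reproduce. The calculation shows what the cut would cost under stated assumptions.

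**Inputs from the documents.** There are 164 patients, 82 per group. Eradication is assumed to be 70% with EAL and 80% with EBTL. The significance level is 0.05, and the cut is at 60. Expected failures are 82 × 0.30 + 82 × 0.20 = 24.6 + 16.4 = 41, or 25% of 164.

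**Assumptions, not in the documents.** The effect of age is linear on the logit, tests are two-sided, both arms are pooled, and the age distribution is as given in each case.

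**Information kept, Normal ages.** Let c = (60 − mean)/SD, let p be the share aged 60 or over, and let φ be the standard Normal density. The share kept is φ(c)² / [p(1 − p)].

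| c | p | Share kept | Share lost | Equivalent patients of 164 |
|---|---|---|---|---|
| 0 | 0.500 | 0.399²/0.250 = 0.637 | 36% | 104 |
| 0.5 | 0.309 | 0.352²/0.213 = 0.581 | 42% | 95 |
| 1 | 0.159 | 0.242²/0.133 = 0.439 | 56% | 72 |

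The 36-56% range therefore belongs to 60 lying between 0 and 1 SD above the mean, for example a mean of 50-60 with SD 10-14.

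**Other distributions.** A younger population loses more: with mean 45 the loss is 59% (SD 14) to 73% (SD 10). For uniform ages the share lost is 1 − 3p(1 − p):
- 20-80 years, p = 1/3: 33%
- 30-80 years, p = 0.4: 28%
- 20-90 years, p = 3/7: 27%

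Across everything tried, the loss runs from about 27% to 73%.

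**Power of the univariate screen.** Simulated trials used n = 164, Normal age with mean 55 and SD 12, and 25% failures. The score test on age in years was compared with the same test on the two-class variable, which is the uncorrected chi-square test.

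| True odds ratio per 10 years | Age in years | Cut at 60 |
|---|---|---|
| 1.5 | about 75% | about 56% |
| 1.3 | about 40% | about 29% |

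These figures vary by a percentage point or two between runs.

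**If the effect is a step at 60.** In the same setting, a step odds ratio of 2.5 gives about 71% power with the cut and 50% with age in years. A step odds ratio of 3 gives about 84% and 65%. The ordering reverses.

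**If each arm is analysed separately.** With 82 patients, power at 1.5 per 10 years is about 45% for age in years and 32% for the cut.

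**The case against.** The strongest objection is that the direction of the loss depends on the shape of the effect, on which the documents are silent. A true threshold at 60 would favour the planned coding, as the step calculation shows. This stands, and it means the loss must be stated conditionally. It does not justify the plan as written, because no reason is offered for expecting a threshold at that age.

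Second, the cut is written into the plan and so is not chosen from the data. That is correct, and no such charge is made.

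Third, recoding age does not by itself remove the gate. Even in years, age would miss the screen about 25% of the time at an odds ratio of 1.5 per 10 years and about 60% of the time at 1.3. This also stands, and it is why the fix must keep age in the model regardless of its univariate result.

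Fourth, the plan does not say whether the arms are pooled. With 82 per arm the analysis is weak under either coding, so the pooled figures are the favourable case.

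A reader might infer that alcohol has the same fault, since it is split by "history of alcohol consumption (<80 g/day or" the higher class. The documents do not support this. The items collected are described only as "including age, sex, medical history, history of smoking, alcohol, coffee and tea consumption", which does not show that grams per day are kept as a number.

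A reader might also infer that the cut leaves the odds ratios of other factors confounded by age. That would require age to be related both to outcome and to another listed factor, and the documents report no such relation.

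**Conclusion.** The point holds as a minor one about age alone. Age is available for every patient, is reduced to two classes without a stated reason, and must then pass a significance screen. If its effect is roughly linear on the logit, the cut costs about 36-56% of the information for Normal ages with 60 lying 0-1 SD above the mean, and about 27-73% over the wider set of assumed distributions. In the pooled mean-55, SD-12 case, the chance of passing the screen drops by about 19 percentage points (75% to 56%) for an odds ratio of 1.5 per 10 years and 11 points (40% to 29%) for 1.3.

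It would be tempting to quote 36-56% as a property of this trial. It is not, since the documents supply neither the age distribution nor the shape of the effect. Nor does the point touch the randomised comparison of eradication rates, adverse events or compliance. It concerns one covariate in a secondary analysis.

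**What to change.** Amend the factor-analysis paragraph to say that age in years enters both the univariate and the logistic analyses as a continuous term, reported as an odds ratio per 10 years. Age should stay in the logistic model whatever its univariate P value. The split at 60 is kept for descriptive tables and as a sensitivity analysis, which also covers a possible threshold at that age.

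The cost is a sentence or two of wording. No new data are needed, and logistic regression is already planned. There are two downsides: some power is lost if the effect really is a step at 60, and one model term is always used when only about 41 failures are expected.
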